The effect of dietary carbohydrate and calorie restriction on weight and metabolic health in overweight/obese individuals: A multi-center randomized controlled trial

(A Randomized, Multicenter, Controlled Trial)

STUDY PROTOCOL

Zhujiang Hospital, Southern Medical University

Nanfang Hospital, Southern Medical University

School of Public Health and Tropical Medicine, Southern Medical University

ABBREVIATIONS

BMI: Body mass index

CRF: Case report form

ECG: Electrocardiogram

BP: Blood pressure

DBP: Systolic blood pressure

SBP: Diastolic blood pressure

HDL-C: High-density lipoprotein cholesterol

LDL-C: Low-density lipoprotein cholesterol

HOMA-IR: Homeostasis model assessment-insulin resistance

TC: Total cholesterol

TG: Triglyceride

WHR: Waist to hip ratio

LC: Low-carbohydrate

CR: Calorie-restricted

NC: Normal control

1. Background and Significance

Obesity and its associated metabolic abnormalities have become a major public health challenge worldwide. It affected 12.0% of adults around the world[23] and 14.0% in China[24]. Obesity is characterized by excessive adipose tissue and is closely related to type 2 diabetes, hypertension and cardiovascular disease[4]. Thus, seeking an optimal effective treatment for obesity is currently a hot topic among researchers.

Dietary interventions have been proven to be an effective treatments targeting weight loss[4-6]. The conventional dietary approach following high/moderate-carbohydrate, low-fat, energy-deficit diet to achieve weight loss is generally accepted and recommended by guidelines[8-10]. Calorie-restricted diet has been recognized as the main component of weight loss intervention[11-12]. In recent low-carbohydrate diet been compared with has conventional energy-restricted diets, and become a popular strategy for weight loss and weight maintains[13-14]. The differences in health benefits between a low-carbohydrate diet and a calorie-restricted diet are of considerable public interest. Several clinical trials assessed the weight loss effects between low-carbohydrate diet and calorie-restricted diet. Several clinical trials assessed the weight loss effects between low-carbohydrate diet and calorie-restricted diet. Dansinger[20] and colleagues found no statistically significant differences between low-carbohydrate diet and calorie-restricted diet during the 12 months intervention. Foster[21, 22] and Stern[19] also reported that there were no significant differences in weight loss between low-carbohydrate diet and calorie-restricted diet at 12 months. In contrast, Samaha[16] found that subjects on a low-carbohydrate diet lost more weight than those on a calorie and fat-restricted diet in 132 severely obese participants during the 6-month study period. Bazzano[15] and Gardner[18] reported that low-carbohydrate diet had significantly greater weight loss than calorie-restricted diet over 12 months intervention. Furthermore, Shai[17] compared the effectiveness of weight loss diets among 322 moderately obese subjects and also found that low-carbohydrate diet would be more effective than calorie-restricted(low-fat) diet over 24 months intervention. Therefore, the reported effects of low-carbohydrate diet versus calorie-restricted diet on weight loss have varied.

However, previous studies have examined the effects of low-carbohydrate, energy deficit diet and calorie-restricted, low-fat diet on weight loss, but most of these trials did not compare the weight loss effects of a calorie-restricted diet alone (calorie-restricted, high/moderate-carbohydrate) with a low-carbohydrate diet alone (low-carbohydrate, non-calorie-restriction). In addition, these studies did not provide evidence that a combination of low-carbohydrate and calorie-restricted diet was more effective for weight loss and reducing metabolic risk factors than calorie-restricted diet or low-carbohydrate diet alone. Therefore, the effects of low-carbohydrate and calorie-restricted diet on weight loss and metabolic risk factors in overweight/obese adults need to be tested in future clinical studies.

2. Specific Aims

In this study, we aim to test the effects on weight loss in overweight/ obese adults by a combination of LC diet and CR diet. We propose to conduct a 12-week clinical trial to evaluate the effects of or LC and CR diet on weight loss. We hypothesize that a combination of LC and CR diet would have a greater weight loss and favorable metabolic effects than LC diet and CR diet alone in overweight/obese adults.

The primary specific aims are:

- 2.1. To test the effect of LC+CR diet over 12 weeks on changes in BMI compared to LC diet and CR diet alone;
- 2.2. To test the effect of LC diet over 12 weeks on changes in BMI compared to CR diet;
- 2.3. To test the effect of LC+CR diet, LC diet and CR diet alone over 12 weeks on changes in BMI compared to the NC group.

The secondary specific aim is:

2.4. To compare the effect of LC+CR diet, LC diet and CR diet control on waist circumference, body fat, and metabolic risk factors.

3. Research Design and Methods

[figure not shown]
3.1. Overall designs

This study is a randomized, multiple-center, parallel group, controlled clinical trial. After screening, all eligible trial participants will be randomly assigned to NC

group, LC diet group, CR diet group and LC+CR diet group (**Figure 1**) for 12 weeks with an allocation ratio of 1:1:1:1. A total of 300 participants will be enrolled. The study will be conducted in the following 13 hospitals in Guangdong Province, China:

- Zhujiang Hospital, Southern Medical University, Guangzhou;
- Huizhou Central People's Hospital, Huizhou;
- Qingyuan People's Hospital, Qingyuan;
- The Third Affiliated Hospital of Guangzhou Medical University, Guangzhou;
- DONGGUAN KANGHUA HOSPITAL, Dongguan;
- Hexian Memorial Affiliated Hospital of Southern Medical University, Guangzhou;
- Guangdong Provincial People's Hospital, Guangzhou.
- Guangdong Second Province Central Hospital, Guangzhou;
- Dongguan People's Hospital, Dongguan;
- Affiliated Hospital of Guangdong Medical University, Zhanjiang;
- The First People's Hospital of Shunde, Shunde;
- The Eighth Affiliated Hospital, Sun Yat-Sen University, Shenzhen;
- Shaoguan First People's Hospital, Shaoguan.

• Figure 1. The schedule for screening

3.2. Statistical power and sample size

The study will enroll 300 participants, who will be randomly allocated to four groups with an equal number of individuals per group:

- NC group
- LC diet group
- CR diet group
- LC+CR diet group

The primary outcome (BMI) will be compared between any two groups at 12 weeks. The sample size calculation was based on the following assumptions:

- Statistical power 85%
- Significance level of 0.05 for the Bonferroni correction of multiple comparisons using a 2-tailed test
- Detectable effect size of BMI = $-0.6 \text{ kg/m}^2[25-28]$
- Standard deviation of BMI = $-0.6 \text{ kg/m}^2[25-28]$

Thus, 60 subjects in each group are required. Assuming a dropout rate of 20%, we will recruit 300 participants and randomly allocate 75 subjects to each group in the proposed clinical trial.

4. Inclusion and Exclusion Criteria

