16.2. Analysis methods

Data will be analyzed according to participants' randomization assignment (intent-to treat). A mixed-effects model will be used to assess the effects of diet programs on the change in BMI and an autoregressive correlation matrix will be used to correct within-participant correlation for repeated measurements. In this model, variables will be assumed to be random effects, and intervention group, time, and their 2-factor interactions, age, sex will be assumed to be estimable fixed effects. PROC MIXED of SAS statistical software, version 9.4 (SAS Institute Inc), will be used to obtain point estimates and SEs of the treatment effects and to test for differences between treatments. Multiple imputations for missing data in the multivariable analyses will be conducted using the Markov chain Monte Carlo method. P-value <0.05 will be considered as statistically significance. Group differences in the study outcomes will be evaluated using the general linear model for continuous variables and the chi-squared test for categorical variables. Data will be presented as least-squares means with 95% confidence intervals (CIs).

17. Training for Study Staff

All study staff (physicians and nurses) will be trained and certified before the study is initiated. The training program will include instruction on questionnaire administration and anthropometrics (height, weight, waist circumference, and hip girth) and blood pressure measurement. A standard questionnaire will be used, which includes personal information (name, sex, age, place of birth, marital status, occupation, education, household income, etc.), medical history, medication use, family history, lifestyle factors (smoking and drinking), physical activity, dietary habits, and menstrual and reproductive history. Anthropometric measurements and blood pressure will be obtained using a standard protocol. The data, including that for dietary record, duration, heart rate, and anthropometric measurements, will be collected and recorded in CRFs by research assistants every week. Body fat mass will be quantified using a body composition analyzer (Jawon Medical, Gyeongsansi, South Korea). All technologists are experienced and blind to randomization of the participants.

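### Optional gain: Holm's or Shaffer's step-down test could replace plain Bonferroni for the six BMI contrasts at no cost in patients, but it adds power only if effects are smaller than the protocol prints

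*Protocol*

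**What the plan says.** Section 3.2 of the protocol sets the scope of the primary comparison: "The primary outcome (BMI) will be compared between any two groups at 12 weeks". Its sample-size assumptions include "Significance level of 0.05 for the Bonferroni correction of multiple comparisons using a 2-tailed test", with 85% power, a difference of 0.6 kg/m² and an SD of 0.6 kg/m² (both printed with a minus sign; read here as magnitudes). It concludes "Thus, 60 subjects in each group are required", raised to 75 for 20% dropout.

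The three primary aims in section 2 give the family. Aim 2.1 is "To test the effect of LC+CR diet over 12 weeks on changes in BMI compared to LC diet and CR diet alone" (two contrasts). Aim 2.2 sets LC against CR (one). Aim 2.3 sets each diet arm against NC (three). Together these are all six pairs, although the protocol never writes the divisor 6.

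Section 16.2 describes a mixed model and states "P-value <0.05 will be considered as statistically significance". It names no multiplicity procedure and no testing order.

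**The concern.** Plain Bonferroni holds each contrast to 0.05/6 whatever the other five show. The six hypotheses are logically linked: if any two arms differ, at most three of the six equalities can still be true. A step-down test uses this. LC+CR against NC is plausibly the largest contrast, and once it is rejected the others face a lighter threshold at the same family-wise error.

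Any power given up falls on aim 2.1, the comparison of the combination with each diet alone, which is the trial's main hypothesis. Bonferroni is the only method named, so it is the one a reader would carry into the analysis. The question is whether the loss is large enough to matter.

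**Working it through.** **Why a step-down test cannot do worse.** Order the six p-values. Bonferroni rejects every p ≤ 0.05/6 = 0.00833. Holm compares the smallest with 0.05/6, the next with 0.05/5, and so on to 0.05/1, stopping at the first failure. Shaffer uses divisors 6, 3, 3, 3, 2, 1. Every p-value that passes 0.05/6 passes its step in either procedure, so both reject all that Bonferroni rejects, and sometimes more.

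**The protocol's own figure.** Two-sided 0.05/6 gives z = 2.638; 85% power gives z = 1.036.

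n per arm = 2 × (2.638 + 1.036)² × SD² / difference² = 2 × 13.50 × 0.36/0.36 ≈ 27.01 (unrounded quantiles), so 28.

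The stated 60 is not reproduced. The dropout step is: 60/0.80 = 75, and 4 × 75 = 300.

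**Bonferroni power on the printed inputs at 60 per arm.** The standard error of a difference is 0.6 × √(2/60) = 0.1095. Then 0.6/0.1095 = 5.48, and 5.48 − 2.638 = 2.84, which gives about 99.8% power.

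**The SD at which 60 per arm gives 85%.** SD² = 60 × 0.36/27.01 = 0.800, so SD = 0.894. This is an assumption, about 49% above the printed 0.6.

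**Power by simulation.** 200,000 trials per pattern, 60 per arm, pooled-variance t tests. Effects are in kg/m², in the order NC, LC, CR, LC+CR. All effect patterns are assumptions; the protocol gives only one detectable difference. Each cell shows Bonferroni / Holm / Shaffer.

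| SD | Effects | Each aim 2.1 contrast, % | Both aim 2.1 contrasts, % |
|---|---|---|---|
| 0.6 (printed) | 0, 0, 0, −0.6 | 99.8 / 99.9 / 99.9 | 99.5 / 99.7 / 99.8 |
| 0.894 | 0, 0, 0, −0.6 | 84.4 / 86.7 / 88.9 | 75 / 79 / 82 |
| 0.894 | 0, −0.6, −0.6, −1.2 | 84.4 / 91.3 / 91.4 | 75 / 86 / 86 |
| 0.6 | 0, −0.3, −0.3, −0.6 | 53 / 63 / 64 | 37 / 49 / 50 |
| 0.6 | 0, −0.6, −0.6, −0.9 | 53 / 66 / 66 | 37 / 54 / 54 |

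The last row can be followed by hand. The three contrasts with NC are almost always rejected, so the first remaining contrast faces 0.05/3 (z = 2.394) instead of 0.05/6. With 0.3/0.1095 = 2.74, power under Bonferroni is Φ(2.74 − 2.638), about 54%. At 0.05/3 it is Φ(2.74 − 2.394), about 63%, and the further relaxation to 0.05/2 brings it to 66%.

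In the third row, plain Bonferroni would need about 71–72 evaluable participants per arm to match the step-down figure for a single contrast. Simulated family-wise error stayed within 5% in every pattern, up to simulation error.

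**The case against.** The strongest reply is that nothing here is wrong. Bonferroni is a valid method. It appears only among the sizing assumptions, and sizing on Bonferroni does not prevent a step-down analysis. The final procedure may also be in an SAP that is not at hand. All of this stands, and it is why the point is optional.

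The second reply is that the gain disappears on the printed figures. That also stands: 99.8% leaves nothing visible to recover. A reader might infer from the step-down argument that this trial would gain clearly more power at its planned size. The documents do not support that, because it requires an SD near 0.9 or an increment well below 0.6, and the protocol states neither. The protocol's figures do conflict, however: its difference and SD imply 28 per arm, while its 85% and 60 imply an SD near 0.89. So 99.8% cannot be taken as settled either. Nor does the protocol explain why the combination's increment over a single diet should be a full 0.6.

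A reader might also infer that the analysis will be needlessly strict. That is not established. Section 16.2 does not carry Bonferroni forward and, read literally, applies no correction at all.

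Third, Bonferroni has simultaneous intervals that agree with its tests, which counts for something because 16.2 promises 95% confidence intervals. This is a real trade-off.

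**Conclusion.** The point holds as an efficiency suggestion. For the six linked week-12 BMI contrasts, Holm or Shaffer controls the same 5% family-wise error as the one method named and is never less powerful.

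The size depends on inputs that the protocol does not settle:

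- On the printed difference and SD, the gain is 0.1 to 0.2 percentage points per contrast.
- If the SD is about 0.89, power for both aim 2.1 contrasts rises by roughly 4 to 11 points, depending on effect pattern and procedure.
- If the SD is 0.6 and the combination adds only 0.3 beyond 0.6 from each diet, it rises by about 17 points (37% to 54%).

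The divisor of six is inferred from the aims. The figures do not show that the trial is underpowered. Nor can the stated 85% be called a lower bound for the step-down test while the inputs behind it do not give 60 per arm; that discrepancy is a separate and more serious matter.

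**What to change.** In section 16.2, name Holm's (or Shaffer's) step-down test over the six week-12 BMI contrasts, at a two-sided family-wise 0.05, as the decision rule for the primary outcome. In section 3.2, refer to that rule, state that the family has six contrasts, and keep Bonferroni as the conservative sizing assumption. If the SAP names a procedure, the two documents should agree. The choice should be fixed before any week-12 comparison between arms is examined.

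This change leaves the sample size as it is. Do not describe 85% as a guaranteed minimum until the difference, SD, power and 60 per arm have been reconciled.

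The cost is wording, plus one loss: simple simultaneous intervals will not match the step-down decisions. Report either unadjusted 95% or Bonferroni intervals, labelled as such, and note that an interval and its test may disagree.

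### The printed sample-size inputs give about 29 per group, not 60: the SD is a negative copy of the effect size, so the 85% power cannot be verified

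*Protocol*

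**What the plan says.** Section 3.2 of the protocol lists the inputs and draws the sample size from them:

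- Comparisons: "The primary outcome (BMI) will be compared between any two groups at 12 weeks".
- Power: "Statistical power 85"%.
- Type I error: "Significance level of 0.05 for the Bonferroni correction of multiple comparisons using a 2-tailed test". The number of comparisons to divide by is not given.
- Effect: "Detectable effect size of BMI = $-0.6" kg/m², citing references 25-28.
- Variability: "Standard deviation of BMI = $-0.6" kg/m², citing the same references.
- Result: "Thus, 60 subjects in each group are required".
- Inflation: "Assuming a dropout rate of 20"%, giving 75 per group and 300 in all.

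Section 3.1 fixes equal groups ("with an allocation ratio of 1:1:1:1"). Section 8.1 defines the primary outcome as the change in BMI from baseline to 12 weeks. The protocol gives no other SD for BMI or for BMI change.

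**The concern.** The variability line cannot be correct as printed, because an SD is never negative. It matches the line above it in value, sign, unit and citations, which suggests that the effect size was copied into the place of the SD. It is also labelled as an SD of BMI, although the outcome is a change in BMI. The effect line uses the same shorthand, so this is loose labelling rather than a second error, but it leaves open which SD was meant.

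Dropping the minus sign does not help. Effect and SD would then be equal, a standardized difference of 1.0, and such a large effect does not need 60 per group at 85% power.

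This paragraph is the protocol's only justification for 300 participants. As it stands, a reader cannot tell whether the trial is far larger than its inputs require or whether the 60 comes from a different, unreported SD. In the second case the true power depends strongly on a number that nobody can check.

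**Working it through.** **Inputs.** All are from section 3.2 unless noted.

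- Difference d = 0.6 and SD s = 0.6, both read as magnitudes.
- Power 85%, so z = 1.036.
- Two-sided test, equal groups (section 3.1).
- Comparisons: any two of four groups gives 4 × 3 / 2 = 6. Aims 2.1 to 2.3 agree, listing 2 + 1 + 3 = 6 contrasts. So alpha = 0.05 / 6 = 0.0083 and z = 2.638.

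**Step 1: the plan's own figure.** For two means, n per group = 2 × (z_alpha + z_power)² × (s/d)².

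2 × (2.638 + 1.036)² × (0.6/0.6)² = 27.007, rounded up to **28**. The exact noncentral-t calculation gives **29**. The stated 60 is not reproduced.

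**Step 2: other readings of the correction.** The divisor is not printed, so the calculation was repeated for other values at 85% power, two-sided, SD 0.6. The last two columns give the SD that would make 60 per group correct.

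| Comparisons | n, normal | n, t | SD implied by n = 60, normal | SD implied by n = 60, t |
|---|---|---|---|---|
| 1 | 18 | 19 | 1.10 | 1.09 |
| 3 | 24 | 26 | 0.96 | 0.95 |
| 4 | 25 | 27 | 0.93 | 0.92 |
| 5 | 27 | 28 | 0.91 | 0.90 |
| 6 | 28 | 29 | 0.89 | 0.88 |

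Other variants also fall short of 60:

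- One-sided tests and 80% or 90% power, with each of these divisors, span 13 to 33.
- A four-group ANOVA at 85% power needs 14 to 26 at alpha 0.05, or 20 to 37 at 0.05/6, depending on the pattern of means.
- Treating 0.6 as the SD of a single BMI measurement, with baseline and week 12 uncorrelated, gives a change SD of 0.6 × √2 = 0.85 and n = 55 (normal) or 56 (t) with six comparisons.

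**Step 3: power of 60 per group with the printed inputs.** With six comparisons it is 99.7% by the t calculation, against the stated 85%.

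**Step 4: sensitivity to the SD.** The SD values below are assumptions, because the value actually used cannot be recovered. All figures are for 60 evaluable per group and alpha 0.0083, by the t calculation.

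| Assumed SD of change (kg/m²) | Power for 0.6 kg/m² | Detectable difference at 85% power (kg/m²) |
|---|---|---|
| 0.6 | 99.7% | 0.41 |
| 0.88 | 85% | 0.60 |
| 0.9 | 83% | 0.61 |
| 1.0 | 73% | 0.68 |
| 1.2 | 52% | 0.82 |

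**Step 5: the dropout step.** 60 / (1 - 0.20) = 75 per group, and 4 × 75 = 300. This part is correct, so the fault lies in the SD line or in the 60 itself.

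**The case against.** The best defence is that this is a reporting slip in a trial that may be adequately sized. If the SD really were 0.6, 60 per group would be more than enough. An SD of 0.9 with six comparisons gives 61 per group by the normal formula, close enough to 60 to make a transcription error plausible. The minus sign might also come from conversion of the PDF. The mixed model with repeated measures, age and sex in section 16.2 is not the simple two-sample test used here, so the cut-offs are approximate.

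Most of this is fair, and it limits what can be claimed. The error does not show that the trial is underpowered. The 0.88 threshold and the Step 4 table hold for six comparisons; with three, the threshold would be about 0.95, and with no correction about 1.09. Six is nevertheless what sections 2 and 3.2 describe.

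The defence does not rescue the 60. Removing a stray sign leaves an SD of 0.6 and a requirement of 28 or 29. Only a different SD reconciles the paragraph, and the protocol gives none. Nor can the point be left to a statistical analysis plan, since the protocol itself states both the inputs and a result that does not follow from them.

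**Conclusion.** The concern holds: the sample-size statement is wrong as written. Its printed SD is impossible, and the same value taken as positive gives 28 (normal) or 29 (t) per group with six comparisons, about half the stated 60. At 85% power, no number of comparisons tried, from one to six, comes near 60. The claimed 85% at 60 per group therefore rests on an SD that is not in the protocol, about 0.88 to 0.89 if six comparisons were used.

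The mismatch follows directly from the printed figures. The lower power values (83% to 52%) rest on assumed SDs of 0.9 to 1.2, on alpha of 0.05/6 and on an unadjusted two-sample test. They show how far power depends on the missing number, not what the trial's power is.

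**What to change.** Correct section 3.2 as follows:

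1. Replace the SD line with the positive SD of the 12-week change in BMI that was actually used, with its source.
2. State the number of comparisons and the resulting level: 0.05/6 = 0.0083, two-sided.
3. Rerun the calculation and print the result with the method used.
4. If 60 evaluable per group is kept, state the power for 0.6 kg/m², or the detectable difference at 85% power, that it gives under the sourced SD. Add a short sensitivity table over a range of SDs. An SD of 0.88 should appear as the sourced value only if a source supports it; otherwise it should be labelled as the value at which 60 per group gives 85%.

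The cost is one rewritten paragraph. The correction does not itself change enrolment, procedures or clinical management, and the dropout step stands. The stated power may become less favourable once the SD is supplied, and the sponsor should then report it as it is.
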